6.1.8. Data Adjustments/Handling/Conventions

All collected data will be presented in Clinical Data Interchange Standards Consortium (CDISC) datasets. Data not subject to analysis according to this plan will not appear in any tables or graphs but will be included only in the CDISC datasets.

All *P* values will be displayed in 4 decimals and rounded using standard scientific notation (e.g., 0.XXXX). If a *P* value less than 0.0001 occurs it will be shown in tables as < 0.0001; similarly, if a *P* value greater than 0.9999 occurs it will be shown in tables as > 0.9999.

Adverse events will be coded using the Medical Dictionary for Regulatory Activities (MedDRA) version 25.0 18 March 2022.

A treatment-related AE is any AE with a relationship to the study drug of possibly, probably, likely, or missing.

For partial AE and medication start dates:

- If the year is unknown, then do not impute the date but assign a missing value.
- If the year is known, but the month or month and day is unknown, then:
 - If the year matches the year of first dose date and the end date (if present) is after first dose date, then impute as the month and day of the first dose date.
 - Otherwise, assign 01 January.
- If the year and month are known, but the day is unknown, then:
 - If the month and year match the month and year of the first dose date, then impute as the day of the first dose date.

- Otherwise, assign 01.

For partial AE and medication end dates:

- If the year is unknown, then do not impute the date but assign as missing value.
- If the year is known, but the month or month and day is unknown, then:
 - If the year matches the year of the last date of the study (date of last contact if subject lost to follow-up; date of completion or early termination otherwise), then impute as the month and day of the last date of the study.
 - Otherwise, assign 31 December.
- If the year and month are known, but the day is unknown, then:
 - If the month and year match the month and year of the last date of the study, then impute as the day of the last date of the study.
 - Otherwise, assign the last day of the month.

These conventions will be applied to AE and medication onset dates and times with the following precaution: if the missing date and time reflect the date and time of onset of an AE, the modified date and time will be constructed to match the first documented date/time post drug administration while preserving the order in which the AE was reported in the eCRF.

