9.7. Concomitant Medication

Prior and concomitant medications will be summarized descriptively by treatment, Anatomical Therapeutic Chemical (ATC) Class Level 4, and Preferred Term using counts and percentages.

Prior medications will be presented separately from concomitant medications. Medications that started before the first application of IP will be considered prior medications whether or not they were stopped prior to the first application of study drug. Any medications continuing or starting after the first application of study drug will be considered to be concomitant. If a medication starts before the first application of study drug and continues after the first application of study drug it will be considered both prior and concomitant.

Medications will be coded using World Health Organization (WHO) Drug Global B3, version March 2022.

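### SAP 6.1.8 sets a start date with only the day missing to the first dose date without checking the end date, so a medication stopped earlier that month gets a start after its end and is misclassified

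*SAP*

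**What the plan says.** SAP 6.1.8 introduces one set of rules with "For partial AE and medication start dates", so adverse events and medications share them.

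- **Month, or month and day, missing.** The first dose date is imputed under the condition "If the year matches the year of first dose date and the end date (if present) is after first dose date". Failing that, 1 January is assigned.
- **Only the day missing.** The rule is "If the month and year match the month and year of the first dose date, then impute as the day of" the first dose. Failing that, the 1st of the month is assigned. The end date plays no part.

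A closing precaution applies only "if the missing date and time reflect the date and time of onset of an AE". It moves such an onset to the first documented time after drug administration. It adds nothing for medications.

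SAP 9.7 then classifies: "Medications that started before the first application of IP will be considered prior medications", and "Any medications continuing or starting after the first application of study drug will be considered to be concomitant". SAP 6.1.1 adds that a medication starting on the date of first treatment counts as postbaseline.

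**The concern.** The SAP applies the end-date check to the less complete date and omits it for the more complete one, and gives no reason. If a medication's recorded end date is earlier in the first-dose month, the day-missing branch imputes a start that the subject's own data show to be impossible. Imputing toward the first dose date is a sensible cautious default when nothing contradicts it. Here a recorded date does.

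At stake is the split between prior medications (Table 14.1.5) and concomitant medications (Table 14.3.8). A product that was properly stopped before Baseline could be listed as used on study. The branch also governs AE onset, so a serious event recorded after consent but before dosing could be moved past the first application.

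**Working it through.** The documents give no figure on this point, so there is none to reproduce. The check applies the rules literally.

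**One record.** The dates are illustrative: first dose 20 June 2022, recorded medication end 10 June 2022.

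| Start as recorded | Branch | Imputed start | Start after end? | Class |
|---|---|---|---|---|
| June 2022, day unknown | day missing, as written | 20 June 2022 | yes, by 20 − 10 = 10 days | not prior; concomitant |
| 2022, month and day unknown | month missing, as written | 1 January 2022 | no | prior only |
| June 2022, day unknown | day missing, with end-date condition | 1 June 2022 | no | prior only |

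**The class in the first row.** The imputed start equals the first dose date, so it is not before first application and the record leaves the prior group. SAP 6.1.1 treats a start on that date as postbaseline, which makes it concomitant under SAP 9.7. If SAP 9.7 is read alone and strictly (before or after), the record falls in neither class. Either way it is wrongly lost from prior use.

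**Is the example special?** In a 30-day month there are 30 × 29 / 2 = 435 pairs of a first-dose day and an earlier end day. As written, all 435 give a start after the end and a concomitant class. With the end-date condition, none does. This shows that the fault occurs whenever its conditions are met. It is not an estimate of frequency.

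**Conditions.** A record is affected only if all of these hold:

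1. The start month and year equal those of first dose.
2. The start day is missing.
3. The end day is known and earlier than first dose in that month.

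If the end day is also missing, SAP 6.1.8 moves the end to the last day of the month, or to the last study date if that lies in the same month. No inversion then arises.

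**Which products can qualify.** The drug must be both started and stopped between the 1st of the month and first dose on day D. Protocol Table 1 (Section 4.7) limits this for subjects who comply with washout:

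- 1 week (medicated shampoos, sedating antihistamines): stop by D − 7, so D is at least 8.
- 2 weeks (topical anti-psoriasis drugs and others): stop by D − 14, so D is at least 15. With D = 20 the whole course must lie within days 1 to 6.
- 4 weeks (etanercept, systemic agents, phototherapy): stop by D − 28, so D must be 29 to 31 and the stop on day 1 to 3.
- 8 weeks or more (adalimumab, infliximab, other biologics): 56 days exceeds any month, so this is impossible.

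**The case against.** The best case against acting is that very little turns on this, and most of that case stands.

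A reader might infer that washed-out psoriasis drugs will appear as prohibited on-study use. The documents do not support that as the typical case. Subjects must have had psoriasis for at least 6 months, and a long-running therapy started in an earlier month goes to the 1st of that month and stays prior. The washout periods leave only brief courses of 1- or 2-week products, and 4-week products almost never.

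A reader might also infer that screening SAEs will become treatment-emergent. Non-serious AEs are collected only after first application, so anchoring their onset to first dose is right. Only pre-dose SAEs are exposed. These are reported within 24 hours of awareness with onset noted, and the subject would still have to be found eligible. The route exists, because SAEs are collected from consent and the closing precaution pushes an unknown onset past dosing, but it is remote.

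Nor does the point reach the Per Protocol population. Important deviations come from a blinded team review (SAP 5) and a data review before lock (SAP 7.2), not from imputed medication dates. Safety data are summarised without inferential tests (SAP 9).

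None of this removes the fault. The day-missing rule gives a result that contradicts a recorded date, and neither 6.1.8 nor 9.7 corrects it for medications.

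**Conclusion.** The point holds as a minor wording error with a definite wrong result. Every record meeting the three conditions gets a start after its end and leaves the prior-medication table. Counting it as concomitant rests on reading SAP 9.7 together with SAP 6.1.1.

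The documents give no count of partial dates, so the number of affected records is unknown. Few are expected, mainly short incidental courses during screening. The effect is confined to Tables 14.1.5 and 14.3.8 and, in principle, the TEAE tables. The co-primary and secondary efficacy tests do not use these dates.

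**What to change.** In the day-missing branch for start dates, add the condition of the neighbouring branch, "and the end date (if present) is after first dose date", and otherwise assign the 1st of the month. If the sponsor prefers on or after first dose, use that in both branches, so that an end date equal to first dose is treated alike. Either wording removes all the inversions above, because they involve only ends before first dose.

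For AEs, also state that the closing precaution does not override a recorded end before first dose; otherwise the pre-dose SAE route stays open.

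Then check the existing AE and medication records for an imputed start later than the recorded end, and correct any found. The cost is one clause, a short qualification for AEs and one data check. SAP version 3.0 already post-dates unblinding, so the change should be documented as made after unblinding. It applies the same way in both arms and leaves efficacy untouched.

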6.2. Special Handling for COVID-19 Disruptions

In the event subjects are unable to complete protocol-specific assessments onsite, study sites may collect data from subjects remotely via telephone and/or by traditional mail or email. The method used for data collection must be clearly documented in the source. Whenever possible, sites should adhere to the protocol visit window for remote data collection. Screening and Baseline/Day 1 visits/assessments must be performed in the clinic and must NOT be completed remotely. If necessary, these visits can be delayed ensuring they are conducted in the clinic and not remotely.

Investigator assessments and subject questionnaires normally completed during on-site visits should be completed on the appropriate paper source documents and entered in the EDC. The following subject assessments/questionnaires are approved to be collected via telemedicine/remote:

- C-SSRS
- PHQ-8/PHQ-A
- Subject Local Tolerability
- Adverse Events
- Concomitant medication

The following Investigator assessments cannot be completed via telemedicine/remote:

- S-IGA
- B-IGA
- PASI

- PSSI
- BSA
- Investigator Local Tolerability
- Subject Weight

Subjects who were affected by COVID-19 disruptions by either missing their Week 8 visit or being discontinued before having a Week 8 visit due to COVID-19 related disruptions will be excluded from the mITT population, as described in [Section 5](#).

7. STUDY SUBJECTS AND DEMOGRAPHICS

7.1. Disposition of Subjects and Withdrawals

Disposition will include tabulations of the number of the screen subjects, the number of screen failures, the number of subjects randomized into each treatment group, the number of subjects who received treatment, subjects completing study, tabulated reasons for discontinuation from the study, including whether the subject did not complete the study due to COVID-19 disruption and reasons, and number of subjects in each analysis population. Disposition will be summarized for all subjects who were entered into database by treatment group and overall.

A listing of subject's disposition will be provided. Information on first screening for subjects who were rescreened, will be presented under the first screening subject identifier.

7.2. Protocol Deviations

A data review will be conducted before database lock by the Medical Monitor and the Sponsor to identify protocol deviations as important or non-important.

The number of subjects with important protocol deviations and/or eligibility will be summarized for each deviation category by treatment group and overall for the subjects in the ITT population. In addition, all the protocol deviations (including important and non-important) associated with COVID-19 will be summarized.

A listing of all protocol deviations will also be provided.

7.3. Demographics and Other Baseline Characteristics

Summary statistics for age, age category (12-17, 18-64 and \geq 65 years old), gender (including child-bearing potential), race, ethnicity, height, weight, BMI, Fitzpatrick Score, and baseline disease characteristics (duration of scalp/body psoriasis at baseline, % BSA affected by disease, S-IGA, B-IGA, PSSI, SI-NRS, WI-NRS, PSD total score, PASI, Scalpdex, DLQI, and CDLQI) will be presented by treatment group and overall, using descriptive statistics (continuous results) or counts and percentages (categorical results) as appropriate.

A summary of treatment history, including history of response, intolerance, or contraindication to topical corticosteroids and/or topical vitamin D derivatives, Apremilast (Otezla), systematic therapy, phototherapy, and psoriasis involvement on knees and/or elbows, face, and genitalia will be provided.

For ordinal variables such as the S-IGA, B-IGA, SI-NRS (average weekly and daily), and WI-NRS (average weekly and daily), summary statistics including the mean, median, Q1, Q3, minimum, and maximum of the ordinal variable will be presented, as well as frequency counts of each level of the ordinal variable.

These analyses will be conducted for the ITT, and Safety populations, except for treatment history summary, which will only be summarized on the Safety population.

A listing of all demographics, analysis population flag, reason not included in the efficacy analysis will be provided.

Medical history for all subjects will be presented in a by-subject listing.

7.4. Exposure and Compliance

The number of expected IP applications will be summarized by treatment group.

The number of IP applications by each subject based on diary data will be summarized using descriptive statistics appropriate for continuous variables.

The amount of IP each subject used based on can weight will be summarized descriptively by treatment group using continuous methods.

The number of days on IP will be summarized descriptively by treatment group.

A subject will be considered compliant with the dosing regimen if the subject applies at least 80% of the expected applications during the treatment period and does not miss more than 3 consecutive doses.

Investigational product application compliance will be calculated based on number of applications divided by the expected number of IP applications. Compliance will be summarized descriptively by treatment group using the following categories:

- $> 100\%$
- $\geq 80\% - \leq 100\%$
- $< 80\%$

A listing of drug exposure, compliance and accountability will also be provided.

8. EFFICACY ANALYSIS

Efficacy analysis will be based on ITT population unless specified otherwise. The randomized treatment arm and strata will be used in the efficacy analysis.

The efficacy analyses that include the stratification factors (pooled sites, baseline S-IGA and baseline B-IGA) will use the strata data as collected in the interactive web response system (IWRS). A table of randomized strata vs. actual strata will be provided if there are any differences.

The order of testing for the co-primary and secondary endpoints is discussed in [Section 6.1.3](#). Other secondary efficacy endpoints are not included in the testing strategy.

Data analyzed using CMH methodology will be based upon the following code:

```
proc freq data=example noprint;
  by <visit>;
  tables <pooled site group> * <BL S-IGA randomization strata > * <BL B-IGA
randomization strata > * <treatment>
  * <outcome> / cmh commonriskdiff(cl=MH) alpha=<0.025 or 0.05>;
  output out=example_stat cmh;
run;
```

If a non-estimable odds ratio and associated p-value occur as part of the multiple testing strategy, the p-value to be used in the testing strategy will be based on a test of a difference in proportions. In cases where the odds ratio and difference in proportion are non-estimable, the stratification factors will be removed. Statistical significance will be concluded at the 2.5% significance level (2-sided) or less, as discussed in Section 6.1.3. Odds ratios, 95% CIs, and 97.5% CIs for the odds ratios and differences in percent will be provided, whenever possible.

Data analyzed using ANCOVA will be based upon the following code:

```
proc mixed data=example;
  by <visit>;
  class <treatment> <pooled site group> <BL S-IGA randomization strata > <BL
B-IGA randomization strata >;
  model <outcome> = <treatment> <pooled site group> <BL S-IGA randomization
strata > <BL B-IGA randomization strata > <baseline value> / alpha=<0.025 or
0.05>;
  lsmeans trtn / alpha=<0.025 or 0.05> pdiff cl;
run;
quit;
```

8.1. Primary Efficacy Analyses

The two co-primary efficacy endpoints of S-IGA Success and B-IGA Success at Week 8 will be analyzed using ITT population.

The S-IGA and B-IGA are ordinal scales with 5 severity grades which are reported only in integers. [Table 4](#) illustrates the description of each severity grade.

Table 4: S-IGA and B-IGA

| Score | Grade | Description |
|-------|--------------|---|
| 0 | Clear | Plaque thickening = no elevation or thickening over normal skin Scaling = no evidence of scaling Erythema = none (no residual red coloration but post-inflammatory hyperpigmentation may be present) |
| 1 | Almost Clear | Plaque thickening = none or possible thickening but difficult to ascertain if there is a slight elevation above normal skin level Scaling = none or residual surface drying and scaling Erythema = light pink coloration |
| 2 | Mild | Plaque thickening = slight but definite elevation Scaling = fine scales partially or mostly covering the lesions Erythema = light red coloration |
| 3 | Moderate | Plaque thickening = moderate elevation with rounded or sloped edges Scaling = most lesions at least partially covered Erythema = definite red coloration |
| 4 | Severe | Plaque thickening = marked or very marked elevation typically with hard or sharp edges Scaling = non-tenacious or thick tenacious scale, covering most or all of lesions Erythema = very bright red coloration; extreme red coloration; deep red coloration |

The co-primary estimands can be described by the following attributes:

Population: Subjects with Scalp and Body Psoriasis

Endpoints: S-IGA Success and B-IGA Success

Treatments: Roflumilast foam 0.3% vs. matching vehicle foam

Intercurrent events: Over the 8-week randomized treatment period, subjects may be exposed to possible known or unknown inter-current events that could impact the estimates of the estimand, such as treatment discontinuation due to a specific adverse effect or a lack of effect. A composite strategy will be implemented that handles subjects who discontinue due to lack of efficacy or adverse event as missing not at random, differently than all other subjects. Subjects who discontinue due to lack of efficacy or adverse event will be considered as non-responders (for MI and nonresponder imputation analyses) or missing (for observed case analyses) for all analysis visits (refer to Section 5.4) on or after the associated analysis visit of the subject's last dose day (refer to Section 6.1.5)

The original primary estimand has been left unchanged but re-labeled as a supplemental estimand and will handle all intercurrent events using a “Treatment Policy Strategy”, including discontinuation due to lack of efficacy or adverse event. Multiple imputation procedures are described in Section 6.1.4.1.2.

Population-level summary: For this study, the primary population summary will be the ratio of

the odds of achieving S-IGA/B-IGA success and also the ratio of the odds for B-IGA success at Week 8 week using ARQ-154 (roflumilast foam 0.3%), relative to the odds of success at Week 8 using the matching vehicle foam. An additional estimand will be the between group difference in the proportion of subjects achieving S-IGA success and the proportion of subjects achieving B-IGA success after receiving 8 weeks of ARQ-154 (roflumilast foam 0.3%) or a matching vehicle foam.

Missing data will be imputed as described in Section 6.1.4. For each imputation dataset, the odds ratio will be obtained from CMH test stratified by the randomization factors (pooled site group, baseline S-IGA category (3 vs. 4) and baseline B-IGA category (2 vs. ≥ 3)). The proportion differences will also be obtained based on stratification factors of baseline S-IGA, baseline B-IGA and pooled site group. SAS® PROC MIANALYZE will be used to combine the estimates from the imputation datasets (Section 6.1.4). These approaches produce estimates which are the combined odds ratio and the proportion difference resulting from adjusting for the possible confounding effects of the three classification factors – pooled site group, baseline S-IGA category (3 vs. 4) and B-IGA category (2 vs. ≥ 3). Randomized stratification factors will be used in the efficacy analysis. S-IGA and BIGA will be tested separately, but each endpoint must be statistically significant at the 2.5% level for the study to be considered a success.

8.1.1. Scalp Investigator Global Assessment (S-IGA)

Categorical Data Analysis

The first co-primary efficacy endpoint is success in S-IGA of disease severity, defined as an S-IGA of “Clear” or “Almost Clear” plus at least a 2-point improvement from baseline at Week 8.

The primary endpoint will be analyzed using a CMH test stratified by pooled site group, baseline S-IGA stratum, and baseline B-IGA stratum. Statistical significance will be concluded at the 2.5% significance level (2-sided) or less, as discussed in Section 6.1.3. Odds ratios, 95% CIs, and 97.5% CIs for the odds ratios will be provided. Additionally, the 95% and 97.5% CIs for proportion of successes in each treatment group will be presented using an extension of Wilson’s method proposed by Lott and Reider⁵. Finally, the proportion difference (using Mantel-Haenszel stratum weights and the Sato variance estimator) and 95% and 97.5% CIs of the risk difference between roflumilast foam 0.3% and vehicle will be presented.

For the primary analysis, missing S-IGA scores will be imputed using multiple imputation as described in Section 6.1.4.1. The CMH analyses will be performed separately for each of the complete analysis data sets, and the results will be combined into one multiple imputation inference (estimated treatment effect and associated CI and *P* value).

A tipping point analysis will be performed as described in Section 6.1.4.2. For the tipping point analysis, a table will be provided that displays the *P* values in the analysis against the range of shift parameters; included in this table will be the shift parameters, odds ratios, 97.5% CIs, and *P* values for the range of shift parameters to provide information on where the analysis tips from significant to non-significant.

